2.3 Correlative objectives

- 2.31 For patients with secretory tumors,
 - 2.311 To examine changes in plasma metanephrine levels and urinary catecholamine and/or metanephrine levels.
 - 2.312 To examine whether lenvatinib-induced changes in plasma metanephrines and urinary catecholamine and/or metanephrine levels during the first cycle of treatment may be associated with objective tumor response.
- 2.32 To examine associations between tumor response and somatic mutational status in archived tumors, or germline mutational status (presence of SDHD, SDHB, RET, VHL, neurofibromatosis type-1).

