4.0 STUDY CALENDAR

4.1 Test Schedule

Tests and procedures ¹				Active Treatment				End of Treatment	
	≤28 days prior to registration	≤14 days prior to registration	≤7 days prior to registration	Cycle 1			Prior to Day 1 of subsequent cycles ³	Every 2 months	
				D1	D3	D10 ²			
Tests and procedures ¹	Window:						±3 days	±7 days	±14 days
Clinical Procedures									
Vital signs, history (including personal/family history for prolonged QTc) and exam, weight, PS		X		X	X	X	X		X
Height		X							
Review of concurrent medications ⁴		X					X		
Pregnancy test ⁵			X						
Blood pressure monitoring ⁶		X		X	X	X	X		
Adverse event assessment		X		X	X	X	X		X
Consultation with endocrinologist, cardiologist, or nephrologist for blood pressure management		X					X		
Hematology: CBC/diff ⁷		X					X		X
Chemistry Panel ⁸		X					X		X
TSH		X					X		
24 hr urine catecholamine and metanephhrines		X					X		
Plasma fractionated metanephhrines		X					X		
Urinalysis ⁹		X					X		
Urine protein/creatinine ratio		X					X		
Genetic counseling and testing at discretion of patient and counselor ¹⁰	X								

¹ All tests and procedures are clinically indicated, unless noted with an R to indicate funding by research

² May be omitted at discretion of treating provider and replaced with telephone call contact.

³ If patient is tolerating treatment well, return visits may be performed over the phone for non-imaging cycles (starting with cycle 3, 5, 7 etc.). During these phone visits the patient status, treatment information, and Adverse Event Assessments must be assessed and recorded. Labs may be done locally and transmitted to Mayo Clinic.

⁴ Concurrent/concomitant medications are reviewed every cycle. Only requested medications are recorded in the study case report forms.

⁵ For women of childbearing potential only. Must be done ≤7 days prior to registration

⁶ Note: 1) daily monitoring of blood pressure is REQUIRED and must be recorded in patient diaries throughout the entire duration of therapy; 2) any systolic BP >150 mm Hg and/or diastolic BP >100 mm Hg must be brought to the attention of treating provider <24h after noted; 3) any systolic BP >200 mm Hg and/or diastolic BP >110 mm HG should prompt immediate cessation of lenvatinib therapy maintained until remediation to <150 mm Hg systolic is accomplished.

⁷ Must include: hemoglobin (hgb), MCV, leukocyte count, neutrophils (ANC), monocyte count, lymphocyte count, and platelet count (PLT)

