6.6 Treatment start

Treatment cannot begin prior to registration and must begin ≤ 14 days after registration.

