Descriptive statistics, and scatter plots will form the basis of presentation of these data both overall and by other outcomes (toxicity, response and survival measures). Correlations between the QOL outcomes and other outcome measures will be carried out by standard parametric and non-parametric tests (e.g. Pearson's and Spearman's rho). Comparison between continuous variables will be made with Wilcoxon rank sum tests, Fisher's exact tests will be used to determine differences between categorical variables, and Log-rank test will be used to test differences between time-to-event outcomes.

16.23 Correlative aims:

16.231 For patients with secretory tumors

To examine changes in urinary catecholamine and metanephrine levels during treatment, time series plots of urinary catecholamines and metanephries levels will be constructed (with patient whose tumor responded to treatment in red and patients whose tumor remained stable or progressed in blue) to visually assess trends prior to treatment discontinuation within and between chemistries as well as difference in trends between those whose tumor responded to treatment and those whose tumor did not.

To examine whether lenvatinib-induced changes in urinary catecholamine and/or metanephrine levels during the first cycle of treatment may be associated with objective tumor response, the fold change from baseline levels for each biomarker will be determined. For each biomarker, a plot of the fold change versus response status will be constructed to visually assess differences between those whose tumor

responded to treatment and those whose tumor did not. If feasible, Wilcoxon rank sum tests will be used to examine whether fold changes in a given biomarker during the first cycle of treatment differs between those whose tumor responded to treatment and those whose tumor did not.

- 16.232 To examine associations between tumor response and somatic mutational status in archived tumors, or germline mutational status in patient's peripheral blood mononuclear cells, (presence of SDHD, SDHB, RET, VHL, neurofibromatosis type-1).
For SDHD, SDHB, RET, VHL, neurofibromatosis type-1, a 95% confidence interval for the difference in proportion of patients who have a documented tumor response among those with that particular biomarker present and proportion of patients who have a documented tumor response among those without that particular biomarker present.

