For α -adrenergic blockade phenoxybenzamine is the preferred drug. The initial dosage is 10 mg once or twice daily, and the dose is increased by 10 to 20 mg in divided doses every 2 to 3 days as needed to control blood pressure. The final dosage of phenoxybenzamine is typically between 20 and 100 mg daily. The patient should be warned about the orthostasis, nasal stuffiness, and fatigue that occur in almost all patients. With their more favorable side-effect profiles and cost-effectiveness, selective α_1 -adrenergic blocking agents (e.g., prazosin, terazosin, or doxazosin) may be used for those patients who are intolerant of the side effects of phenoxybenzamine or cannot afford phenoxybenzamine. Ultimately, the choice of the agents is at the discretion of the hypertension specialist.

The β -adrenergic antagonist should be administered only after α -adrenergic blockade is effective (with near-normal BP) because with β -adrenergic blockade alone hypertension may be more severe from the unopposed α -adrenergic stimulation. β -adrenergic blockade is indicated to control the tachycardia associated with both the high concentrations of circulating catecholamines and the α -adrenergic blockade. The clinician should exercise caution if the patient is asthmatic or has congestive heart failure. Chronic catecholamine excess can produce a myocardiopathy that may become evident with the initiation of β -adrenergic blockade, resulting in acute pulmonary edema. Therefore, when the β -adrenergic blocker is administered, it should be used cautiously and at a low dose. For example, a patient is usually given 10 mg of propranolol every 6 hours to start. On the second day of treatment, the β -adrenergic blockade (assuming the patient tolerates the drug) is converted to a single long-acting dose of a

cardioselective β -blocker. The dose is then increased as necessary to control the tachycardia (goal heart rate is 60-80 beats per minute).

Metyrosine, a catecholamine synthesis inhibitor, may be used in patients with particularly high metanephrenes/normetanephrenes and/or for difficult to control hypertension prior to initiation of lenvatinib. Typical doses may be up to 1-2 grams per day, but dose escalation is often limited by sedation.

Metyrosine may also be used if there is significant concern for lenvatinib-induced catecholamine release following initiation of therapy.

Orally Administered Drugs for Initial α - and β -Adrenergic Blockade

Drug	Dosage, mg/day*	Side effects

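### The first-cycle biomarker comparison in 16.231 takes no account of metyrosine started between the two samples, which can mask an association and, if use differs clearly by response, create one

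*Combined protocol and SAP*

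**What the plan says.** Objective 2.312 asks whether marker changes attributed to lenvatinib "during the first cycle of treatment may be associated with objective tumor response". Section 16.231 carries this out as follows: "the fold change from baseline levels for each biomarker will be determined". Fold change is then plotted against response status, and "If feasible, Wilcoxon rank sum tests will be used to examine whether fold changes in a given biomarker during the first cycle of treatment" differ between responders and non-responders. There is no covariate, stratum, exclusion or sensitivity analysis for other drugs, and section 12 does not list metyrosine among the descriptive factors.

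In the section 4.1 calendar, the row "24 hr urine catecholamine and metanephhrines" and the row for plasma metanephrines have one pre-treatment entry, in the column for the 14 days before registration. The next entry is before Day 1 of later cycles, within 3 days either way. Section 6.6 adds: "Treatment cannot begin prior to registration and must begin ≤ 14 days after registration".

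Appendix IV D.3 states: "Metyrosine, a catecholamine synthesis inhibitor, may be used in patients with particularly high metanephrenes/normetanephrenes", and also for hypertension that is hard to control, before lenvatinib starts. It continues: "Metyrosine may also be used if there is significant concern for lenvatinib-induced catecholamine release following initiation of therapy". No passage requires metyrosine to be started, or its dose to be stable, before the baseline marker sample.

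**The concern.** A drug that the protocol itself describes as blocking catecholamine synthesis acts on the pathway being measured. If it starts after the baseline sample and before the cycle 2 sample, any fall it causes enters 16.231 as part of lenvatinib's effect. One listed reason for using it is a high marker level, so the baseline result may be what prompts the prescription.

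What is at stake is the interpretation of Hypothesis 2 and objective 2.312. Metyrosine spread evenly over responders and non-responders adds noise and hides a real association. Metyrosine concentrated in one group shifts that group and can imitate or cancel an association. The planned plots separate patients by response only, so a reader could not tell the two sources apart.

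**Working it through.** **Timing.** Baseline may be 14 days before registration and the first dose 14 days after it: 14 + 14 = 28 days at most. The next sample comes at the end of a 28-day cycle, so without delays the two samples can be 28 + 28 = 56 days apart, plus the 3-day window. Metyrosine may start anywhere in that interval.

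**The plan's own figures.** The documents give no sample size, power or significance level for this analysis, so there is nothing to reproduce. They cap the trial at 23 eligible patients and do not say how many will have secretory tumors.

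**Illustration.** Every input is an assumption:
- 14 secretory patients, 5 responders and 9 non-responders;
- log fold change normal, SD 0.4;
- where lenvatinib has an effect, it halves the marker in responders only (log shift 0.693);
- metyrosine multiplies the marker by 0.5 (range 0.7 to 0.3), acting additively on the log scale;
- exact two-sided Wilcoxon test at 5%.

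Figures come from 3,000 simulated trials per setting (Monte Carlo standard error at most √(0.25/3000) = 0.009). A larger rerun agreed within that error.

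*Masking at equal use.* If a proportion p in each group starts metyrosine with log shift d, the variance rises by p(1 − p)d². With p = 0.3 and d = 0.693 the increase is 0.21 × 0.480 = 0.101. The SD goes from 0.40 to √(0.16 + 0.101) = 0.51, and the standardized difference from 0.693/0.40 = 1.73 to 0.693/0.51 = 1.36.

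| Metyrosine use | Effect on marker | Power |
|---|---|---|
| none | – | 0.76 |
| 30% in both groups | ×0.7 | 0.69 |
| 30% in both groups | ×0.5 | about 0.53 |
| 30% in both groups | ×0.3 | about 0.31 |

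*False association.* With no lenvatinib effect, equal use leaves the two distributions identical. Unequal use shifts the group means apart by (difference in use) × d.

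| Use, responders v non-responders | Mean log shift at ×0.5 | False-positive rate at ×0.5 |
|---|---|---|
| none | 0 | 0.04 |
| 30% v 30% | 0 | 0.04 |
| 20% v 10% | 0.07 | about 0.05 |
| 40% v 20% | 0.14 | 0.06 to 0.07 |
| 60% v 10% | 0.35 | 0.20 |

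At 60% v 10% the rate runs from about 0.09 (×0.7) to 0.29 (×0.3). Reversing the imbalance gives similar rates.

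*A second set of assumptions* (SD 0.5; 4 v 8, 5 v 10 and 7 v 16; metyrosine lowering the marker by 30% to 70%) shows the same pattern:
- Equal 30% use keeps false positives at 0.03 to 0.06. It cuts power from 0.50–0.58 to 0.24–0.53 with 12 to 15 patients, and from about 0.80 to 0.47–0.75 with 23.
- Use of 10% in responders v 50% in non-responders gives false positives of 0.06 to 0.28 and cuts power to 0.04–0.38 with 12 to 15 patients.

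**Excluding patients whose metyrosine changed** (first set of assumptions). At equal 30% use, 5 × 0.7 = 3.5 and 9 × 0.7 = 6.3 patients remain on average, and power is about 0.46. At 60% v 10%, 5 × 0.4 = 2.0 and 9 × 0.9 = 8.1 remain, and power is about 0.29. With 2 v 8 only the most extreme ordering is significant: p = 2/C(10,2) = 2/45 = 0.044.

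**The case against.** The strongest reply is that this is a correlative aim, mainly graphical, with a test run only if feasible and no decision attached. Confounding by concomitant drugs in a small uncontrolled series can be reported as a limitation. That limits the weight of the point but does not remove it, since the plan as written gives the analyst no means of showing the confounding.

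The timing is also a maximum. Blood pressure must be controlled before registration, a hypertension specialist must see the patient in the preceding 14 days, and blockade runs for at least 7–14 days before dose 1. Metyrosine given for resistant hypertension may therefore often be in place by the baseline sample. That is fair, but no rule secures it, and use prompted by a high marker result or by concern about release can come later.

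Exposure is partly captured: section 7.1 puts blood pressure drugs on the CRF and the patient diary lists other medication. Whether metyrosine counts as a blood pressure drug is not stated, section 4.1 limits the CRF to requested medications, and no analysis uses the data.

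A reader might infer more than the documents support:
- That a false association is to be expected. D.3 selects on marker level, hypertension and concern about release, not on response. Differential use is plausible but not shown, and mild imbalance barely moves the error rate.
- That metyrosine's effect is known to be large. The documents give its mechanism but no effect on the measured levels.
- That alpha- and beta-blockade distort the markers in the same way. The documents do not say so.
- That the metyrosine-free comparison should be the main one. At equal 30% use and ×0.5 its power is about 0.46, against about 0.53 for all patients, so restriction is a trade-off.

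**Conclusion.** The concern holds in a limited form. Section 16.231 treats an unadjusted fold change as lenvatinib's effect, while Appendix IV lets a drug acting on the same pathway start between the two samples. Masking needs no imbalance; a false association needs metyrosine use that differs clearly by response. The size is unknown, because the documents give neither frequency of use, nor effect on the markers, nor the number of secretory patients. The simulated figures show what is possible under stated assumptions and are not estimates for this trial. The primary endpoint, the Simon decision rule, the secondary endpoints and safety are unaffected. The change is worth making because it is cheap and because dates not recorded during the trial may not be recoverable afterwards.

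**What to change.** 1. Ask for metyrosine start, stop and dose-change dates by name on the CRF, so that capture does not depend on how the drug is classed.
2. In 16.231, define the biomarker baseline as the last available sample before the first lenvatinib dose. Only one pre-treatment sample is now scheduled, so this shortens the gap only where a later one exists. An extra sample shortly before the existing Day 1 visit would be optional.
3. Mark metyrosine users and periods on the time-series and fold-change plots.
4. Keep the all-patient comparison as planned. Add a prespecified sensitivity comparison excluding patients with a metyrosine start, stop or dose change between the two samples, and state that its power is low.

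The cost is one CRF item, a few lines of analysis text and some plot annotation, plus one sample per secretory patient if the optional draw is added. No change is proposed to who receives metyrosine or when.

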11.4 Measurement of Effect

11.41 Target Lesions & Target Lymph Nodes

- Measurable lesions (as defined in Section 11.21) up to a maximum of 5 lesions, representative of all involved organs, should be identified as “Target Lesions” and recorded and measured at baseline. These lesions can be non-nodal or nodal (as defined in 11.21), where no more than 2 lesions are from the same organ and no more than 2 malignant nodal lesions are selected.
Note: If fewer than 5 target lesions and target lymph nodes are identified (as there often will be), there is no reason to perform additional studies beyond those specified in the protocol to discover new lesions.
- Target lesions and target lymph nodes should be selected on the basis of their size, be representative of all involved sites of disease, but in addition should be those that lend themselves to reproducible repeated measurements. It may be the case that, on occasion, the largest lesion (or malignant lymph node) does not lend itself to reproducible measurements in which circumstance the next largest lesion (or malignant lymph node) which can be measured reproducibly should be selected.
- Baseline Sum of Dimensions (BSD): A sum of the longest diameter for all target lesions plus the sum of the short axis of all the target lymph nodes will be calculated and reported as the baseline sum of dimensions (BSD). The BSD will be used as reference to further characterize any objective tumor response in the measurable dimension of the disease.

- Post-Baseline Sum of the Dimensions (PBSD): A sum of the longest diameter for all target lesions plus the sum of the short axis of all the target lymph nodes will be calculated and reported as the post-baseline sum of dimensions (PBSD). If the radiologist is able to provide an actual measure for the target lesion (or target lymph node), that should be recorded, even if it is below 0.5 cm. If the target lesion (or target lymph node) is believed to be present and is faintly seen but too small to measure, a default value of 0.5 cm should be assigned. If it is the opinion of the radiologist that the target lesion or target lymph node has likely disappeared, the measurement should be recorded as 0 cm.
- The minimum sum of the dimensions (MSD) is the minimum of the BSD and the PBSD.

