16.12 Operating Characteristics

The largest tumor response rate for which there would be little interest in pursuing further studies of this lenvatinib regimen in patients with progressive malignant pheochromocytoma or paraganglioma is 10%. The smallest tumor response rate for which there would be interest in pursuing further studies of this lenvatinib regimen in patients with progressive malignant pheochromocytoma or paraganglioma is 30%. The study design proposed below yields a 85% chance of detecting that the true tumor response rate is at least 30% at a 0.15 significance level when the true tumor response rate is at least 10%

16.121 Stage 1: Enter 6 eligible patients. If no tumor responses are documented among these 6 patients within the first 6 cycle of treatment, we will consider the regimen lacking in sufficient antitumor activity to recommend further testing in this patient population and terminate further enrollment. If at least one response is observed among these 6 patients within the first 6 cycles of treatment, we will proceed to Stage 2.

16.122 Stage 2: Enter an additional 17 eligible patients. If three or fewer tumor responses are documented among all 23 eligible patients within the first 6 cycle of treatment, we will consider the regimen lacking in sufficient antitumor activity to recommend further testing in this patient population. If four or more tumor responses are documented among all 23 eligible patients within the first 6 cycle of treatment, this will be considered of the regimen to have promising antitumor activity in this patient population.

We anticipate enrolling a minimum of 6 and a maximum 23 eligible. At the close of stage 1 or stage 2 enrollment, if more patients than planned have been enrolled only the first 6 eligible patients or the first 23 eligible patients enrolled, respectively, will be used to evaluate the decision rule. We anticipate accruing 2 additional patients (25 total) to account for patients found to be ineligible after signing a consent or who refused to start study treatment after signing a consent form.

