16.13 Power and Significance Level

Assuming that the number of tumor responses is binomially distributed, the probability of declaring that this regimen warrants further studies (i.e. statistical power) under various tumor response rates and the probability of stopping

accrual after the first stage can be tabulated as a function of the true tumor response rates as shown in the following table.

If the true tumor response rate is	10%	15%	20%	25%	30%
Then the probability of declaring that the regimen warrants further study is...	0.15	0.37	0.59	0.75	0.85
And the probability of stopping at the completion of stage 1	0.53	0.38	0.26	0.18	0.12

16.14 Accrual Time and Study Duration:

No similar studies have been conducted for comparison. Based on our anecdotal experience from referrals of patients from outside institutions who would otherwise fit eligibility criteria we believe we will be able to enroll 4 to 8 patients per year at our institution (Mayo clinic). We believe we can complete accrual within the proposed 3-year period.

16.2 Analysis Plan:

16.21 Primary Endpoint:

Ninety-five percent confidence intervals for the true response proportion will be calculated according to the approach of Duffy and Santner (Duffy and Santner 1987).

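### The biomarker and mutation analyses use tumor outcome only as responder yes/no; a rank analysis of best percent change should be added beside them

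*Combined protocol and SAP*

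**What the plan says.** Objective 2.312 asks whether first-cycle changes in catecholamines or metanephrines are associated with objective tumor response in secretory tumors. Objective 2.32 asks about tumor response and mutation status.

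- **Section 16.231, plots.** The time-series plots use one color for responders and one for all other patients, whether stable or progressed. For the first-cycle change: "For each biomarker, a plot of the fold change versus response status will be constructed to visually assess differences between those whose tumor" responded and those whose tumor did not.
- **Section 16.231, test.** "If feasible, Wilcoxon rank sum tests will be used to examine whether fold changes in a given biomarker during the first cycle of treatment" differ between the same two groups.
- **Section 16.232.** For each gene the plan gives "a 95% confidence interval for the difference in proportion of patients who have a documented tumor response", comparing patients with and without the mutation. It names no interval method and no test.
- **Section 11.41.** The baseline sum of dimensions (BSD) and the post-baseline sum (PBSD) are both calculated and reported: "The BSD will be used as reference to further characterize any objective tumor response in the measurable dimension of the disease". Section 11.431 requires target lesions to be re-measured at each evaluation, section 11.1 sets evaluations every 8 weeks in the first year, and criterion 3.13 requires measurable disease at entry.
- **Section 16.12.** "We anticipate enrolling a minimum of 6 and a maximum 23 eligible" patients. The biomarker aim uses only those with secretory tumors, and section 17.32 makes both genetic components optional.

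No power, significance level, effect size or subset size is stated for any correlative aim.

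**The concern.** Partial response is a cut at a 30% decrease from BSD. In these analyses a patient whose tumors shrank by 28% is therefore grouped with one who progressed. In a small sample that discards information which the trial records anyway.

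Two things are at stake. The biomarker comparison loses power to detect a real association. It can also become uninformative: with very few responders no arrangement of the data reaches 0.05, and the plan names no fallback test. Hypothesis 1 counts attenuated growth as well as regression, so shrinkage short of the threshold is of interest to this trial. The RECIST cut is appropriate for the primary endpoint and is not questioned there.

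**Working it through.** **1. The plan's own figures.** The only stated operating characteristics are for the primary endpoint (section 16.13): 6 patients, stop at 0 responses; 23 in total, success at 4 or more. Exact two-stage binomial probabilities of declaring activity at true rates of 10, 15, 20, 25 and 30% are 0.149, 0.368, 0.585, 0.748 and 0.852. Early-stop probabilities, (1 − p)^6, are 0.531, 0.377, 0.262, 0.178 and 0.118. The table in the plan reproduces. It says nothing about the correlative aims.

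**2. Smallest attainable p-value of the planned Wilcoxon test.** With k responders among n patients and no ties, the smallest two-sided exact p is 2/C(n, k).

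- 1 of 12: 2/12 = 0.167.
- 2 of 12: 2/66 = 0.030.

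The chance that the planned test cannot reach 0.05, summing binomial probabilities over every k with 2/C(n, k) > 0.05:

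| Secretory patients (assumed) | 30% response | 20% response |
|---|---|---|
| 8 | 56% | 80% |
| 10 | 15% | 38% |
| 12 | 9% | 27% |

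With exactly 4 responses in 23, the threshold for success, and 12 secretory patients, the chance that at most 1 responder is secretory is [C(12,0)·C(11,4) + C(12,1)·C(11,3)] / C(23,4) = (330 + 1,980)/8,855 = 26%.

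**3. Power when one variable defines both response and the continuous outcome.** Log fold change and tumor change are bivariate normal with correlation rho. The responders are the 30% with the most shrinkage. The level is two-sided 0.05, with 40,000 runs per cell. Entries are planned Wilcoxon → Spearman.

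| n | rho 0.4 | rho 0.5 | rho 0.6 |
|---|---|---|---|
| 12 | 0.13 → 0.22 | 0.19 → 0.33 | 0.27 → 0.49 |
| 16 | 0.17 → 0.30 | 0.26 → 0.46 | 0.38 → 0.64 |
| 23 | 0.26 → 0.43 | 0.41 → 0.64 | 0.58 → 0.83 |

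This flatters the continuous analysis. In the trial, response must be confirmed at least 4 weeks later (section 16.11) and also depends on new lesions and non-target disease. When 10% of patients progressed by new lesions unrelated to the biomarker (n = 12, 18 and 23, rho 0.5 to 0.6), the gain fell to 7 to 11 points.

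**4. The choice of scan matters.** Six 28-day cycles are 168 days, or 24 weeks, so scheduled scans fall at weeks 8, 16 and 24. Section 1.232 gives a median time to response of 3.5 months in medullary thyroid cancer: 3.5 × 30.4 = 106 days, about 15 weeks, well after the first scan. Let the 8-week change correlate r with the change that determines response (r is not in the documents; 3,000 runs per cell):

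| Case | Planned | r = 0.9 | r = 0.8 | r = 0.7 | r = 0.6 |
|---|---|---|---|---|---|
| n = 23, rho 0.6 | 58% | 73% | 61% | 46% | 34% |
| n = 12, rho 0.6 | 28% | 41% | 31% | 24% | 17% |
| n = 12, rho 0.5 | 19% | 25% | 23% | 19% | 13% |

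For n = 23 and rho 0.6 the difference is 73 − 58 = +15 points at r = 0.9, but 46 − 58 = −12 at r = 0.7.

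**5. Scan-by-scan trajectories with confirmed response.** At a 30% response rate, n = 12 or 23 and rho 0.4 to 0.6, Spearman on the 8-week change altered power by about −4 to +20 points. Spearman on best percent change over the first 6 cycles gained about 4 to 29 points and was ahead in every case. Gains were smaller when some patients progressed by new lesions.

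**6. Mutation aim.** With 6 carriers among 23, 30% response and a 1 SD shift, the chance of excluding zero is 0.37 with a Newcombe interval. It is 0.34 for significance by Fisher's test and 0.46 for a Wilcoxon test on percent change. Over 5 to 9 carriers, response rates of 20 to 40% and shifts of 0.8 to 1.5 SD, the gain is −4 to 22 points against Newcombe and 9 to 34 against Fisher. With 3 carriers among 23 it is −7 to 13 and 6 to 26.

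**The case against.** The strongest defense is that the plan answers the question it asks. Objectives 2.312 and 2.32 and Hypothesis 2 are all worded as tumor response, so a responder comparison fits them, and replacing it would change the question. These are also exploratory, plot-led analyses on which no primary or secondary conclusion depends. Both points stand. They are why the continuous analysis belongs beside the planned one, not in its place.

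A reader might infer several stronger things that the documents do not support:

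- **A loss of 10 to 30 points across all correlative aims.** That range comes from treating one variable as both response and outcome, and it does not carry over to mutations. Section 16.232 plans an interval of unnamed method, carrier counts are unknown, and the gain can be nil or negative.
- **The first 8-week scan as the natural main outcome.** Step 4 shows that it can do worse than the planned test.
- **The feasibility condition reflects too few responders.** The plan gives no reason; few secretory patients or missing assays would explain it equally well.
- **The biomarker test is bound to fail.** With 2 responders in 12 it can reach p = 0.030. The continuous analysis is not strong in small subsets either: 0.33 at n = 12 and rho 0.5.

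**Conclusion.** The point holds as a modest improvement to exploratory analyses. Sections 16.231 and 16.232 use only response status, although a graded outcome can be derived from data already recorded. For the biomarker aim the continuous analysis gains about 4 to 29 points of power, assuming a 30% response rate, 12 to 23 secretory patients, a correlation of 0.4 to 0.6 and a two-sided 0.05 level. The gain is toward the lower end if some patients progress by new lesions. The planned test also cannot reach 0.05 with 1 responder in 12. For the mutation aim the direction and size of any gain are uncertain. Nothing here affects the primary endpoint, its threshold or the two-stage rule.

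**What to change.** **Section 16.231.** Keep the planned plots and the Wilcoxon test. Add beside them, for each biomarker, a Spearman correlation with 95% CI and scatter plot. It relates first-cycle log fold change to best percent change from BSD over the first 6 cycles, the window already used for the decision rule. Rank patients with a new lesion, unequivocal non-target progression or death before any response as worst. State how patients with no post-baseline measurement and none of these events are handled. Use the 8-week change only as a sensitivity analysis.

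**Section 16.232 (optional).** Beside the difference in response proportions, report the Hodges-Lehmann difference in best percent change with a 95% CI, without any power claim. Name the interval method for the proportions.

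**Cost.** A few sentences and a little programming; no new patients, scans or samples. There is one more exploratory result per marker. Best change slightly favors patients with more scans, including responders, who have the extra 4-week scan under section 11.33. Fixing the window and ranking rule before the data are seen avoids a data-driven choice later.
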